4.0 Study Aims

4.1 Primary Aim: Treatment Effectiveness. To evaluate the effectiveness of XR-NTX vs. O-NTX in producing a primary good clinical outcome, defined as abstinence or moderate drinking (≤ 2 drinks/day, men; ≤ 1 drink/day, women; and ≤ 2 heavy drinking occasions/month), during the final 20 of 24 weeks of primary care-based Medical Management for alcohol dependence.

Hypothesis: The rate of this good clinical outcome will be approximately twice as great among participants receiving XR-NTX compared with those receiving O-NTX.

4.2 Secondary Aim 1: Cost Effectiveness. To estimate the incremental cost effectiveness of XR-NTX vs. O-NTX both in conjunction with primary care-based Medical Management.

Hypothesis: XR-NTX treatment will be more cost effective than O-NTX.

Secondary Aim 2: Patient-Level Predictors of Effectiveness. To identify patient-level characteristics associated with effectiveness in both arms.

5.0 Study Design: A Randomized Comparative Effectiveness Trial to Evaluate XR-NTX vs. O-NTX for Alcohol Dependence in Primary Care

We propose a pragmatic randomized controlled trial to compare the effectiveness and incremental cost-effectiveness of XR-NTX vs. O-NTX as a component of primary care-based Medical Management of alcohol dependence among 234 adults. The 24 week treatment trial will assess monthly treatment retention, self-reported drinking outcomes, biomarkers, and costs. The primary effectiveness outcome is a moderate drinking good clinical outcome, defined as abstinence or moderate drinking (≤ 2 drinks/day, men; ≤ 1 drink/day, women, and ≤ 2 heavy drinking occasions/month), during weeks 5-24. A long-term follow-up assessment at week 48 will gather further drinking and cost data. The MM visit schedule and research assessment visits will occur as follows over 48 weeks (Table 2):

Table 2. Visit Frequency (weeks)	0	1 ⁺	3	5 ⁺	7	9 ⁺	13 ⁺	17 ⁺	21 ⁺	25	26	48
XR-NTX vs. O-NTX + MM visits	x [#]	x [#]	x	x	x	x	x	x	x	x	x [*]	
Research-only assessment visits							x [#]			x [#]		x [#]

- *Safety documentation research visit
- # Compensation provided
- + Medication Dispensed

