Cost-effectiveness analysis requires estimates of costs and estimates of effectiveness. Consequently, we will use primary data analyses from this study (Specific Aim 1 in the proposal) to inform costs and effectiveness estimates in the short-term, and we will synthesize these short-term estimates with published reports that allow us to estimate the longer-term, downstream costs and effects of the changes in alcohol consumption observed in Specific Aim 1. We will alternatively use societal and payer perspectives for assessing costs, and we will use the standard discount rate of 3% for costs and benefits.⁹⁰ The discount rate reflects the time preference with regard to costs and benefits (i.e., a dollar today is worth more to most people than an inflation-adjusted dollar at some time in the future). All costs will be inflated to 2011 US \$ using alternatively the consumer price index (CPI) for all goods and services and the CPI for Medical services (reflecting the ongoing debate over whether the Medical services CPI overestimates inflation because of the difficulty of discriminating the effect of service improvement from service inflation).

Short-term estimates of costs and effectiveness of XR-NTX compared with O-NTX. Short-term estimates of costs and effectiveness will be obtained from primary analysis of data from the trial proposed in Aim 1, using a combination of pre-specified medical record and survey endpoints. Cost assessment will be conceptually similar to recently published analyses of the COMBINE interventions,^{36,37,38} and will include medical and non-medical costs as well as payer and societal costs. Effectiveness assessment will include alcohol consumption measures as described elsewhere in this proposal, as well as quality of life. Quality of life will be assessed using the EQ-5D. The EQ-5D is among the most commonly used quality-of-life measure for informing cost-effectiveness analyses because it has minimal respondent burden, is well validated, and it yields utilities (preference-based measures on a scale of 0 to 1), the desired input for cost-effectiveness models. Because costs are skewed, incremental costs will be assessed using ordinary least squares (OLS) and median regression models with covariates for treatment intervention and other relevant factors, and conditional models may be used because of cost data that may include "zeros."

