Longer-term estimates of costs and effectiveness. To estimate the comparative effectiveness of XR-NTX relative to O-NTX over longer time horizons than are reflected by our data, we will incorporate these short-term results within a state-transition (Markov) computer simulation of outcomes that enables a cohort of hypothetical alcohol-dependent patients to be followed over time until death, and to be exposed to alternative alcohol interventions for specified time durations beyond the week 24 assessment. We will develop this simulation expressly for this proposal, drawing on our experience creating, validating, and using other computer simulations assessing the impact of alcohol interventions on long-term costs and benefits.^{91,92,93,94,95} The simulation will be able to aggregate the lifetime benefit of remitting alcohol dependence for designated periods of time using trial endpoints (e.g. frequency of heavy drinking days), and also can quantify benefits of the levels of improvement short of full remission (e.g. if alcohol

dependence remits but the patient still is an at-risk drinker). The simulation will estimate lifetime costs and benefits over a lifetime horizon, measured in both life-years and quality-adjusted life-years. (Quality-adjusted life years is a preference-based, quality of life metric that considers quality of life simultaneously with quantity of life, and instantiates the notion that a typical person would trade away some quantity of life to get a greater quality of life.) In sensitivity analyses we will consider time horizons shorter than lifetime (10 year and 20 year) because these horizons are sometimes preferred by decision makers, even though the longer, lifetime horizon is advocated by the Panel on Cost-Effectiveness in Health and Medicine.⁷⁷

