Further considerations of the cost-effectiveness approach: The above simulation will assume that the costs and benefits observed in the trial have varying levels of persistence. In the most pessimistic scenario, any treatment effect observed in the trial would wane rapidly after the trial follow-up period, and therefore any benefits that accrue in the long-term would be attributable to the short-term effect, or, in the more optimistic scenario, any treatment effect observed would persist indefinitely, as long as the treatment is continued. Therefore, the simulation would aggregate incremental benefits of magnitude observed in the trial that are assumed to persist as long as the treatment is continued. The most optimistic, albeit unrealistic, scenario is that the treatment effect will persist indefinitely after the trial concludes, and no additional treatment would be necessary. Because this scenario is unrealistic, we will only perform analyses along these lines as sensitivity analyses; however, we will analyze scenarios in which persistence of treatment effect requires select treatment “boosters” of variable duration and frequency.

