To aggregate the impact of remission of partial and/or complete alcohol dependence, the simulation will require estimates of the impact of alcohol dependence and other alcohol use disorders (e.g. at-risk consumption and harmful consumption) on quantity and quality of life, and on costs. These estimates will be based on published reports that have aggregated the impact of alcohol on the morbidity and mortality and costs of specific diseases with substantial risk attributable to alcohol (e.g., hypertensive heart disease, cirrhosis of liver, oral cancers, etc).⁹⁶ In addition, simulation input will also draw on published reports that have aggregated the impact of alcohol on morbidity, mortality, and costs of non-medical sequelae of alcohol consumption (e.g., motor vehicle collision, arrests)⁹⁷ As in our previously published simulation work, we develop the computer simulation for this proposal by incorporating the standard, stepwise procedure of *specification* (defining the structure and mathematical relationships of the variables in the model), *verification* (otherwise known as “debugging”; making sure the model performs consistently with expectations across a wide range of inputs, including “stress tests” when inputs may be deliberately set to extreme, clinically unrealistic values in an attempt to unmask flaws in the model), *parameterization* (inputting variable estimates based on relevant data or expert opinion), *calibration* (making sure model output is similar to observed clinical output in relevant circumstances), and *validation* (testing model performance in circumstances or clinical populations distinct from those used for model development).

Uncertainty: we will estimate 95% confidence intervals around point estimates of incremental cost-effectiveness using standard approaches in which vectors on the cost-effectiveness plane are identified corresponding to the 2.5th and 97.5th percentiles of incremental cost-effectiveness. We will also create corresponding acceptability curves, which denote the probability that a particular program or programmatic decision is favorable given a particular willingness to pay for health benefits.

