If the trial is negative, what’s the purpose of Aim 2? It might be observed that, if an intervention is not effective, it is meaningless to estimate its cost-effectiveness. Therefore, it might appear that the scientific validity of Aims 1 and 2 are inter-dependent. However, in the event that Aim 1 produces negative results, we will employ the computer simulation developed for Aim 2 for a slightly different purpose. Rather than using the simulation to estimate the cost-effectiveness of XR-NTX versus O-NTX, we will instead use the simulation to ask “what is the minimum level of incremental effectiveness required for an intervention to deliver sufficient value?” so that Aim 2 remains scientifically relevant and useful for decision makers. For example, even if XR-NTX does not deliver significant improvements in effectiveness compared to O-NTX, we would use the simulation to infer what levels of incremental effectiveness would be necessary to deliver sufficient value, given particular assumptions about incremental costs. For example, if a new intervention cost \$100/month more than O-NTX, how many fewer heavy-drinking days would it need to reduce compared to O-NTX in order to deliver sufficient value (incremental cost-effectiveness ratio < \$100,000/QALY)? That way, simulation results can inform future trial design. This approach is detailed in our recent publication,⁹⁸ and is concordant with principles of value-of-information analysis.⁹⁹

10.3 Secondary Aim 2: Patient-Level Predictors of Effectiveness. The multivariate models described for Aim 1, while testing the main and subsidiary hypotheses, will also be used to identify patient characteristics associated with treatment success. We hypothesize a priori that there will be less robust effectiveness in both arms among women and African Americans, while pre-treatment abstinence, voluntary specialty alcohol treatment and Alcoholics Anonymous involvement (patients are not directly referred to ancillary treatment), and presence of the Asp40 OPRM1 SNP will be associated with treatment effectiveness. We also hypothesize that these positive associations will be more pronounced within the XR-NTX arm due to the sustained medication adherence following each injection. We note, however, that these analyses will be exploratory, as the study is not powered to carefully test these secondary hypotheses.

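### After a negative primary result the plan replaces the long-term XR-NTX vs O-NTX cost-effectiveness estimate with a minimum-effect question, although Secondary Aim 1 carries no such condition

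*Combined protocol and SAP*

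**What the plan says.** Section 4.2 states Secondary Aim 1 as estimation, with no condition on the primary result: "To estimate the incremental cost effectiveness of XR-NTX vs. O-NTX both in conjunction with primary care-based Medical Management".

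Section 10.2 plans two layers of analysis.

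- **Short term.** "Short-term estimates of costs and effectiveness will be obtained from primary analysis of data from the trial proposed in Aim 1". These cover costs, drinking measures and EQ-5D utilities.
- **Long term.** A state-transition model follows a hypothetical cohort until death: "The simulation will estimate lifetime costs and benefits over a lifetime horizon", with 10- and 20-year horizons as sensitivity analyses. It works from what the trial shows. In the scenario where the effect lasts as long as treatment continues, "the simulation would aggregate incremental benefits of magnitude observed in the trial". Benefit is accumulated "using trial endpoints (e.g. frequency of heavy drinking days" being the example given.

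For uncertainty, 10.2 plans 95% intervals on the cost-effectiveness plane and acceptability curves, which show "the probability that a particular program or programmatic decision is favorable given a particular willingness to pay".

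The paragraph of 10.2 on a negative trial (which calls the cost-effectiveness aim Aim 2) then changes the use of the model: "Rather than using the simulation to estimate the cost-effectiveness of XR-NTX versus O-NTX, we will instead use the simulation" to ask what minimum incremental effect would deliver sufficient value. It does not define a negative result. Its example is the case "even if XR-NTX does not deliver significant improvements in effectiveness compared to O-NTX".

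**The concern.** The negative-trial paragraph moves from a result that is not significant to an intervention that is not effective. A difference that misses significance may still be sizeable. Cost-effectiveness is a question of expected costs, expected benefits and decision uncertainty, and it does not need a rejected null hypothesis. The intervals and acceptability curves already planned in 10.2 are the right way to show an uncertain effect.

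The rule is a substitution, not an addition. When it applies, the trial gives no lifetime, 10-year or 20-year comparison of the two drugs, and no cost per QALY beyond what the within-trial data support. Section 1.0 puts the drugs at about $1,100 and $100 per month and makes their relative benefits and costs a key question. The substitute analysis is illustrated with an extra cost of $100 per month, not the roughly $1,000 that separates these two drugs.

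A second consequence follows from keeping the estimate only after a significant result: the observed effects that survive are, on average, larger than the true effect.

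**Working it through.** **Inputs.** Section 9.0 gives 20% success on O-NTX and 40% on XR-NTX, 117 per arm, Fisher's exact test, and power of 0.84 at 100 per arm and 0.90 at 117 per arm. It also says that the projected rates are not well established, so smaller true differences are fair sensitivity cases. The significance level and sidedness are not stated; two-sided 0.05 is assumed.

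**Method.** Let X and Y be the successes on XR-NTX and O-NTX, independent Binomial(n, p₁) and Binomial(n, p₀). For every pair (x, y), compute the two-sided Fisher p-value and call the pair significant if p ≤ 0.05. Then:

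- power = Σ P(x)P(y) over significant pairs;
- chance that the long-term estimate is dropped = 1 − power;
- mean observed difference when it is kept = Σ P(x)P(y)(x − y)/n ÷ Σ P(x)P(y), both sums over significant pairs with x > y.

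**The plan's own figures.** At 20% vs 40% this gives 0.844 with 100 per arm (stated 0.84) and 0.901 with 117 per arm (stated 0.90). Both reproduce, which supports the assumed level.

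**Results at 117 per arm, binary primary outcome.**

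| True rates (O-NTX vs XR-NTX) | True difference | Power | Long-term estimate dropped | Mean observed difference when kept |
|---|---|---|---|---|
| 20% vs 40% (design) | 20 points | 0.901 | 9.9% | 21.1 points |
| 25% vs 40% | 15 points | 0.643 | 36% | 18.5 points |
| 30% vs 40% | 10 points | 0.311 | 69% | 17.0 points |

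The kept difference is on average 21.1/20 = 1.06, 18.5/15 = 1.23 and 17.0/10 = 1.70 times the truth. If the estimate is reported in every case, this factor is 1.

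**Smallest observed gain that keeps the estimate.** Suppose 24 of 117 succeed on O-NTX (20.5%). Then 38 on XR-NTX gives p = 0.054 and 39 gives p = 0.039. The threshold is 15 patients, or 15/117 = 12.8 points. An observed gain of 14 patients, 14/117 = 12.0 points, would lose its lifetime estimate.

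**What the rule reaches and what it leaves.** Set side by side within 10.2, the negative-trial paragraph redirects only the simulation. The formula for the incremental ratio, the short-term costs, the drinking effects and EQ-5D carry no condition, and economic data are collected to week 48 (8.3). The lifetime, 10-year and 20-year results come only from the simulation, so these are what is lost.

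**The case against.** The strongest reply is that little is lost. A within-trial incremental ratio with its uncertainty remains planned whatever the primary result, and the fallback is openly pre-specified. If the design assumptions hold, the rule applies in about one trial in ten and the kept effect is only about 6% too large. Kept results would also come with intervals, acceptability curves and pessimistic persistence scenarios. All of this stands as a limit on the size of the problem. It does not explain why a pre-specified estimate should disappear after a non-significant test, and intervals computed after selection do not correct for it.

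A reader might also infer more than the documents support, in three ways.

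- **That Secondary Aim 1 as a whole is answered only after a positive trial.** It is not; the short-term part is unconditional.
- **That the lifetime ratio after a positive trial is too low by a known percentage.** The inflation above is for the binary outcome. The model may use heavy drinking days, and the documents give no correlation between that measure and the binary outcome.
- **That the plan states a p < 0.05 rule.** It does not define a negative result. Non-significance is the natural reading of its example, and the missing definition is itself a gap.

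**Conclusion.** The concern holds for the long-term part of Secondary Aim 1. Section 10.2 replaces the lifetime, 10-year and 20-year comparison of XR-NTX with O-NTX after a negative primary result, while the aim in 4.2 is unconditional.

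The chance of losing that comparison is about 10% if the design rates are right, and rises to 36% and 69% as the true difference falls to 15 and 10 points. These figures rest on three assumptions: negative means not significant; the level is two-sided 0.05; and Fisher's test, the stated basis for power, stands in for the planned covariate-adjusted logistic regression. The upward selection of the kept effect is small at the design rates and material below them. It is an illustration for the binary outcome, not an estimate of bias in the lifetime ratio.

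The primary analysis, safety and data collection are not affected. This is a free improvement to a named secondary aim.

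**What to change.** In 10.2, state that the simulation will be run with the observed cost and effect differences and their joint uncertainty, whatever the primary result. Report net benefit and the acceptability curve in every case, and the incremental ratio where it is stable; net benefit avoids a ratio that becomes erratic when the effect difference is near zero. Keep the minimum-effect analysis as an addition, not a replacement. With that change, the long-term estimate no longer depends on how a negative result is defined.

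The cost is SAP wording only. The simulation is built in either case, and no further patients, visits or data are needed.

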Lead-in drinking abstinence (3 days prior to initiating medications) will be analyzed a priori as a predictor of effectiveness in both medication arms. A participant's ability to abstain from drinking prior to an initial XR-NTX injection may predict treatment response and is highly relevant to the initiation of naltrexone treatment in monitored detox settings,⁴⁵ though we did not observe this same association in our smaller XR-NTX primary care pilot, which is described below and included few patients with pre-treatment abstinence or recently discharged from a detox unit.² Our pilot did find a strong association between persons involved at baseline or who became involved during primary care XR-NTX treatment with specialty alcohol treatment and/or Alcoholics Anonymous. We will be able to carefully track prior detox admissions, pre-treatment abstinence, and concurrent 12-step and specialty alcohol treatment involvement in the proposed trial in order to estimate associations with treatment effectiveness. Likewise, while we will recruit only participants willing to try either form of naltrexone, participants will be queried at baseline for a strong preference of oral vs. XR.

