7.7 Research-only Assessment Visits

As in any large clinical trial of usual care, some participants in both arms will not be present for all scheduled treatment visits. In an attempt to 'de-link' complete cost, utilization, and longitudinal drinking data collection from a naturalistic observation of these same usual care patterns, we will conduct 3 Research-only Assessment visits at week 13, 25 and 48. These visits will not hinge on a participant's treatment retention status, will be heavily incentivized to encourage participation (\$100 for time and travel), and will be conducted preferably in-person but alternatively by telephone if a participant is otherwise unwilling or unable to appear in clinic. These visits will be carefully scheduled apart from MM treatment visits, which are otherwise not incentivized beyond the provision of no-cost care and medication, so as to minimize the influence of extra assessments, attention, and the monetary research participation incentive on a participant's willingness to continue with MM. Participants will be paid \$20 for the initial screening visit after completion of all research assessments and \$20 after completing the randomization visit.

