The primary outcome measure of this study is a binary measure of success defined by abstinence or moderate drinking only, as measured by the TLFb, with drop-outs from MM and research-only assessments assumed to have resumed baseline rates of heavy drinking, and therefore defined as good clinical outcome failures. Our analytic approach will be an intention-to-treat comparison of all randomized participants (N=234). The analysis will utilize a logistic regression with an indicator variable for treatment and covariate terms for baseline potential prognostic indicators that are not stratified for at randomization, including AA ethnicity, lead-in abstinence, medication preferences, baseline drinking severity, in-trial specialty treatment involvement, clinical site, and OPRM1 genotype. If the coefficient of treatment is significant the null hypothesis of equal treatment effect is rejected. Odds ratios will be calculated to quantify the risk to treatment failure of significant predictors (Secondary Aim 2: Patient-Level Predictors of Effectiveness: To identify patient-level characteristics associated with effectiveness in both arms). To differentiate time to a good clinical outcome failure, we will use a "cure model." The form of a cure model is $H(t) = 1 - p + pS(t)$; where $H(t)$ is the probability of failure at a time greater than t , p represents the probability of failure, and $S(t)$ the distribution of time to failure, conditional on failure occurring. The parameters will be estimated based both on Kaplan Meier methods and parametrically. The equality of the values of p for the two treatment arms will be tested using a nonparametric likelihood ratio test. For the parametric test, a logistic will be used to model p and a Weibull survival distribution will be used to model time to failure, $S(t)$. Both allow the use of covariates, which will complement the above logistic regression approach.

As originally proposed, naltrexone appears most effective at reducing heavy drinking, as opposed to producing complete abstinence, and all traditional alcohol treatment trial clinical endpoints, including continuous drinking and heavy drinking variables, as well as the CDT biomarker, which is specific for heavy drinking, are of great interest, and will be reported in the primary publication from this trial. In addition, rates

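### Aim 2 uses specialty and Alcoholics Anonymous involvement that arises during the trial as a predictor of the weeks 5–24 outcome, so its odds ratio can depart from 1 in either direction with no true effect

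*Combined protocol and SAP*

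**What the plan says.** - **The predictor.** Section 10.3 (Secondary Aim 2) lists "voluntary specialty alcohol treatment and Alcoholics Anonymous involvement (patients are not directly referred to ancillary treatment" among the characteristics expected to go with effectiveness. It sets no window for when involvement counts.
- **The model.** The Aim 1 models "will also be used to identify patient characteristics associated with treatment success". In section 10.1 the logistic regression's covariates, introduced as baseline indicators, include "baseline drinking severity, in-trial specialty treatment involvement, clinical site, and OPRM1 genotype". That covariate is specialty treatment only; the AA in the same list refers to ethnicity.
- **12-step involvement.** This comes from section 3.6, which plans to track "concurrent 12-step and specialty alcohol treatment involvement in the proposed trial in order to estimate associations with treatment effectiveness".
- **The pilot.** Section 3.6 cites a strong association for "persons involved at baseline or who became involved during primary care XR-NTX treatment with specialty alcohol treatment and/or Alcoholics Anonymous", which pools involvement before and after the start of treatment.
- **Missing outcomes.** Section 10.1 analyses the outcome "with drop-outs from MM and research-only assessments assumed to have resumed baseline rates of heavy drinking, and therefore defined as good clinical outcome failures". This could mean leaving either type of visit or both.
- **Follow-up.** Section 7.7 says of the research-only visits at weeks 13, 25 and 48: "These visits will not hinge on a participant's treatment retention status".
- **Referral.** Section 7.3 has Medical Management (MM) support 12-step involvement and make specialty referrals on relapse or treatment failure. Section 7.8 stresses Alcoholics Anonymous for non-responders and urges detox and specialty care on those doing badly.

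No landmark, time-dependent coding, baseline-only definition or rule for involvement unobserved after loss is given.

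**The concern.** Exposure and outcome are recorded over the same weeks, and two features of the plan tie them together without any effect of involvement on drinking.

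First, someone lost at week 8 has eight weeks in which involvement can be recorded; someone followed throughout has 24. The first is a failure by rule and only the second can be a success. Recorded involvement is therefore concentrated among those eligible to succeed.

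Second, failure itself leads to involvement, because the plan directs or encourages non-responders towards more care. That concentrates involvement among failures.

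At stake is a directional a priori hypothesis. Section 1.0 asks whether patient characteristics can inform treatment choice, and an odds ratio produced by recording and referral patterns could be read as an answer. This point concerns the predictor estimate, not the comparison of the two naltrexone arms.

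**Working it through.** **Plan's own figure.** The documents give no figure for this predictor. The success rates used below come from section 9.0, whose power statement reproduces: exact two-sided Fisher power at alpha 0.05 (assumed; not stated) for 20% vs 40% is 0.844 at 100 per arm and 0.901 at 117 per arm, against the stated 0.84 and 0.90.

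**Inputs.** Success S is 40% on XR-NTX and 20% on O-NTX (section 9.0). Assumed: proportion F still followed at week 24, weekly uptake w of 1–3%, constant hazards, and no effect of involvement on drinking.

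**Formulas.** Loss hazard h = −ln(F)/24; uptake hazard λ = −ln(1−w).
- Involved, if followed throughout: q = 1 − (1−w)^24.
- Involved, if lost: r = 1 − [h/(h+λ)] × [1 − e^(−24(h+λ))]/(1−F).
- Involved, among failures: f = [(F−S)q + (1−F)r]/(1−S).
- Odds ratio = [q/(1−q)]/[f/(1−f)].

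**Worked case, XR-NTX, F = 0.75, w = 0.02.** q = 0.384. h = 0.01199, λ = 0.02020, so r = 1 − 0.3724 × 0.5382/0.25 = 0.198. f = (0.35 × 0.384 + 0.25 × 0.198)/0.60 = 0.307. Odds ratio = 0.624/0.443 = 1.41. For O-NTX with F = 0.65, f = 0.301 and the odds ratio is 1.45. Pooling equal arms: f = (0.60 × 0.307 + 0.80 × 0.301)/1.40 = 0.303, odds ratio 1.43.

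**Upward bias alone.** Ranges are for w = 1–3%. Rejection is for a Wald test at N = 234, nominal 5%.

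| Followed, XR / O | Pooled OR | Rejection | XR arm | O arm |
|---|---|---|---|---|
| 85% / 80% | 1.18–1.27 | 8–13% | 1.18–1.26 | 1.18–1.27 |
| 75% / 65% | 1.36–1.52 | 14–31% | 1.34–1.50 | 1.37–1.55 |
| 45% / 20% | 2.6–3.3 | 69–98% | 2.3–2.8 | 3.0–3.7 |

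The last row corresponds to section 9.0's treatment completion rates (40–50% and under 20%). It applies only if recording stops at treatment drop-out.

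**Adding the downward bias.** Let failures take up care at twice the rate (2λ in place of λ). The result depends on who does so and when:

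| Doubled uptake applies to | 85% / 80% | 75% / 65% |
|---|---|---|
| All who will fail, throughout | 0.48–0.54 | 0.62–0.63 |
| Failures who stay in follow-up, throughout | 0.59–0.60 | 0.76–0.86 |
| Failures who stay, only after failing (failure time uniform over weeks 5–24) | 0.85–0.88 | 1.03–1.15 |

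**Recovering unobserved involvement.** A separate simulation at 30% loss, 30% pooled success and 30% uptake over 24 weeks gives 1.39. If half of the lost have later involvement recovered from records it gives 1.17; if all do, 1.00.

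**Alternative definitions, no true effect.** Baseline-only involvement gives 1.00 with 5% rejection. A week-4 landmark gives 0.99–1.01 with 5% rejection at 10%, 30% and 50% loss, including when failures triple their uptake after failing. The landmark fails if those who will later fail already take up care faster before week 4. At doubled uptake, success and failure odds are (1 − 0.99^4)/0.99^4 = 0.041 and (1 − 0.99^8)/0.99^8 = 0.084, a ratio of 0.49.

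**The case against.** **Follow-up is separated from treatment.** Section 7.7 pays $100 for research-only visits and allows telephone contact, section 8.0 places the Economic Form 90 at them, and section 8.3 adds hospital-system records. This stands, and it limits the upward bias to people lost to every source. At 10–20% loss it is small. A reader might put the 45%/20% completion rates in for follow-up and conclude that the bias is large; the documents do not support that.

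**The sign is not determined.** A reader might infer that involvement is bound to appear beneficial. Sections 7.3 and 7.8 create an opposing force that can cancel or reverse the association, so a positive result is not guaranteed. This stands, but it leaves the estimate no easier to interpret.

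**The arm contrast.** Section 10.3 also predicts stronger associations on XR-NTX, and a reader might infer that this is biased too. In the lighter-loss settings the gap between arms is negligible. Where it is appreciable it rests on assumed heavier O-NTX loss and runs against the prediction. No arm-contrast claim is warranted.

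**The analysis is exploratory.** Section 10.3 says so and gives lack of power as the reason. That lowers the stakes, but a larger sample would not remove this bias. Nor do the documents say that this particular estimate will set treatment advice.

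**Conclusion.** The point holds in this form: involvement arising during the trial is an uninterpretable predictor of the weeks 5–24 outcome. Drop-out biases it upward, failure-triggered care biases it downward, and the plan has no safeguard against either.

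With no true effect and success calibrated to 40%/20%, the pooled odds ratio is about 1.2–1.3 at 15–20% loss and 1.35–1.5 at 25–35% loss. It is larger only if recording stops at treatment drop-out. It is about 0.5–0.6 in the two lighter-loss settings if all who will fail take up care at twice the rate throughout, and nearer 1 (0.85–1.15) if the extra uptake starts only after failure in those still followed.

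The structure comes from the documents. Loss, uptake and the size of failure-triggered uptake are assumptions, so the direction in this trial cannot be predicted. The pilot association offers no independent support, because it pooled baseline with later involvement.

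**What to change.** 1. In sections 10.3 and 10.1, define the predictor as involvement at baseline, from the week-1 Economic Form 90, in all randomised participants. Confirm that the form as used captures Alcoholics Anonymous as well as specialty treatment; the documents describe it only as covering treatment history.
2. As a secondary analysis, use a landmark: involvement by the end of week 4, from the week 3 and week 5 MM notes, in those still followed at week 5, against the weeks 5–24 outcome. State how a missed week-5 visit is handled. Note that the analysis assumes uptake by week 4 is unrelated to later prognosis.
3. Report later involvement only descriptively or as a time-varying covariate. Do not report ever being involved during the trial as a predictor of success.
4. Reconcile the section 10.3 statement that patients are not directly referred with the referral wording in section 7.3.

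**Cost.** The baseline definition needs only a change of wording, since the form is already scheduled. Fewer people will count as involved, so precision falls: at 1–3% weekly uptake, new involvement by week 4 is 1 − 0.99^4 = 3.9% to 1 − 0.97^4 = 11.5%, or about 9 to 27 of 234 before losses. The landmark also depends on involvement being recorded in the MM notes, because the next Economic Form 90 is not due until week 13.
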